2 PROTOCOL SYNOPSIS

C 4 1	TO 4 1
TILL 17	1111
Study	11116
~ • • • • • • • • • • • • • • • • • • •	

Effects of A3309, an Ileal Bile Acid Transport Inhibitor, on Gastrointestinal and Colonic Motor Functions in Patients with Functional Constipation

Study code

A3309-003

Principal Investigator

[name] M.D.

Professor of Medicine and Physiology,

Division of Gastroenterology and Hepatology,

Medical Director, Strategic Alliances, Mayo Clinic

Study period	Phase of development
Estimated date of first patient enrolled: January 2010	П
Estimated date of last patient completed: November 2010	

Study design

This is a single-center, randomized, parallel group, double-blind, placebo-controlled, dose response, pharmacodynamic and pharmacokinetic study evaluating the effects of A3309 on gastric, intestinal and colonic transit in patients with functional constipation. Doses of 15 or 20 mg A3309 or matching placebo will be administered orally once daily for fourteen (14) consecutive days.

Aim

To assess the dose related effects of A3309 on small bowel and overall colonic transit and bowel function in patients with functional constipation.

Primary endpoint:

Colonic geometric center at 24 h as measured by scintigraphy, as compared to placebo.

Secondary endpoints:

- 1. Colonic filling at 6 h measured by scintigraphy, as compared to placebo.
- 2. T_{1/2} of ascending colon emptying measured by scintigraphy, as compared to placebo.
- 3. Colonic geometric center at 48 h measured by scintigraphy, as compared to placebo.
- 4. $T_{1/2}$ of gastric emptying of solid
- 5. Assess the effects on stool frequency and consistency based on the Bowel Pattern Diary and effects on symptom parameters coupled to constipation as well as the overall treatment effect, as compared to placebo based on a six question survey given at the end of the pre-treatment period and the post-treatment period.
- 6. Evaluate the pharmacokinetic (PK) and pharmacodynamic characteristics for each dose of A3309.
- 7. Assess the safety and tolerability of A3309 administered as an oral tablet.

Number of patients planned

Twelve female patients with functional constipation in each treatment group for a total of 36 patients.

Diagnosis and main eligibility criteria

Patients with diagnosed functional constipation will be recruited from the local community by public advertisement placed within areas of Mayo Clinic or by a targeted mailing of an informational letter.

Methodology

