11.3 Schedule of Visits

Visit 1 Study Entry

Potential study patients will arrive at the Charlton 7 CRU fasting for the previous eight hours. Patients will be required to sign the ICF after review and explanation of the study and after all questions have been answered. Inclusion and exclusion criteria will be accurately reviewed.

After reviewing and signing a patient ICF, they will have a brief interview (including demographics, medical history and current medications) and a physical examination performed by a study physician. If the results of a normal rectal examination to exclude the possibility of an evacuation disorder are not documented within the previous two years by a qualified gastroenterologist, this exam will be performed

⁴ Laboratory safety assessments include clinical chemistry (ALT; Albumin; Alkaline phosphatase; AST; Bilirubin, total; Calcium; Chloride; C-Reactive Protein; Creatinine; GGT; Glucose; Potassium; Protein, total; Sodium; Urea; Uric acid), hematology (hemoglobin; hematocrit; MCV; platelet count; RBC count; WBC count with differential), coagulation studies (Activated partial prothrombin time aPPT; Prothrombin time PT), urinalysis (blood; glucose; ketones; leukocytes; nitrites; pH; protein), drugs of abuse urine screen (alcohol; amphetamines; barbiturates; benzodiazepines; cocaine; opiates; phencyclidine; tetrohydrocannibinol). The drugs of abuse urine screen is performed once at Visit 1; the other laboratory tests are performed at Visit 1, Visit 6 and Visit 7.

⁵ Blood samples for pharmacodynamics including C4 and a lipid panel of total cholesterol, HDL, LDL and triglycerides are obtained at Visits 1, 4 and 7.

⁶Females of child bearing potential are required to have a negative pregnancy test result within 48 hours prior to the receipt of radiation. Females who are status post-tubal ligation, post-hysterectomy or post-menopause are exempted from this requirement

⁷ A six question survey concerning constipation symptoms and treatment efficacy will be given at Visit 3, the end of the pre-treatment period, and again at Visit 6, the end of the treatment period.

⁸An abbreviated transit scintigraphy with scans obtained at 4 and 24h is performed at Visit 2. A full transit with scans obtained at 0, 30 min, 60 min, 90 min, 2, 3, 4, 5, 6, 7 and 8 hours after taking study medication for 12 consecutive days at Visits 4-6.

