24 STATISTICAL METHODS

24.1 Statistical considerations

An analysis of covariance (ANCOVA) will be used to compare transit parameters and patient bowel pattern diary summaries (i.e., stool frequency, mean stool consistency and mean ease of passage scores) among the treatment groups. The covariates considered for inclusion in the analyses are age, body mass index (BMI) and the corresponding baseline (pre-treatment) bowel pattern diary summaries. If necessary a suitable transformation for potential skewness in the distributions of measured responses or heterogenous variation amongst the treatment groups may be used (i.e., ANCOVA on ranks or square root transformed stool frequency.

If the ANCOVA test for overall treatment effects for a given response has a p value less than or equal to 0.10, then both the 15 mg and 20 mg doses will be compared to placebo using Dunnett's Test.

Since each of the primary endpoints assesses a separate hypothesis regarding the effects of A3309, no adjustment in the alpha level for testing multiple types of endpoints is anticipated, and a two-sided significance level of 0.05 will be used in each ANCOVA model.

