24.6 Stool frequency and stool consistency

Patients are asked to keep a daily bowel pattern diary documenting the number of stools and the consistency (Bristol Stool Scale (28)) of each stool. These are averaged as number of bowel movements or consistency of bowel movements per day per patient. Number of bowel movements and consistency are subsequently averaged over the study periods (i.e. run-in and treatment) per patient. The ANCOVA will be used to assess treatment effects on each of these two measures separately, using the corresponding run-in values as covariates. In addition, treatment effects on specific constipation symptoms, considered as discrete categorical responses, will be evaluated by a contingency table analysis of the post-treatment responses based on the final post-treatment bowel pattern diaries and questionnaires concerning constipation symptoms and treatment efficacy.

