34.5 Patient bowel pattern diary

Daily Diary	Date				
Please record the time the	ne study medication	n was taken:_	am		
If you had no bowel mov	ements today, plea	se check this box:	no bowel mo	vement today	
	Describe the consistency of bowel movement	Describe the ease of passage of bowel movement	How much did you strain during the bowel movement?	Did you feel like you completely emptied your bowels?	Did you feel like you had a sensation of obstruction and/or blockage during the bowel movement?
	1 Hard lumps 2 Lumpy sausage 3 Cracked sausage 4 Smooth sausage 5 Soft lumps 6 Mushy 7 watery	1 Manual Disimpaction 2 Enema needed 3 Straining needed 4 Normal 5 Urgent wopain 6 Urgent w/pain 7 Incontinent	 Not al all A little bit More straining than not A great deal An extreme amount 	1 No 2 Yes	1 No 2 Yes
1 am hr. min pm					
2 am hr. min pm					
3 am hr. min pm					
4 am hr. min pm					
5 am hr. min pm					
6 am hr. min pm					
7 am hr. min pm					
8 am hr. min pm					
Have you had any unusual	events today?	No 🗌	Yes (complete be	elow)	
Event		loderate / Severe	Resolved / Ongoin		
Event		loderate / Severe loderate / Severe	Resolved / Ongoin Resolved / Ongoin	-	
Have you taken any atypica	Il medications toda	v? No □	Yes (complete be	elow)	
Medication		cation	Medicati		
Dose		Dose		ese	
Time(s)	Ti	me(s)	Time	(s)	

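### Section 24.6 sends per-movement diary symptoms to a contingency table without stating the unit of analysis and without using the run-in values

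*Combined protocol and SAP*

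**What the plan says.** The bowel pattern diary (34.5) has eight timed rows a day, one per bowel movement. Each row asks "How much did you strain during the bowel movement" (five levels), "Did you feel like you completely emptied your bowels" (no/yes) and "Did you feel like you had a sensation of obstruction and/or blockage during the bowel movement" (no/yes). The diary has no daily or per-patient version of these three items.

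Section 24.6 reduces two diary measures to one value per patient: "Number of bowel movements and consistency are subsequently averaged over the study periods (i.e. run-in and treatment) per patient". These go to ANCOVA with the run-in value as covariate. Section 24.1 lists the diary summaries for ANCOVA as "stool frequency, mean stool consistency and mean ease of passage scores", which adds ease of passage but not straining, emptying or blockage.

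Symptoms are handled differently. Section 24.6 treats them as categorical, and they "will be evaluated by a contingency table analysis of the post-treatment responses based on the final post-treatment bowel pattern diaries" together with the questionnaires. It names no unit, no rule for turning several diary entries into one response, no test, no time window for the final diaries and no baseline adjustment.

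The questionnaire is a separate instrument. It is completed before treatment at Visit 3 "and again at Visit 6, the end of the treatment period" (footnote 7 to Table 5), so each patient gives one post-treatment answer per item.

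**The concern.** A standard contingency-table test treats its entries as independent. Movements from the same woman tend to resemble each other, and what is randomised is the woman. If movements fill the table, the test can reject because patients differ from one another, with no difference between treatments. Pooling also weights each patient by her number of movements, which the drug is intended to change.

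The other natural reading is one categorised response per patient. It avoids clustering but needs a rule (last, worst, any or majority response), and none is given. It also discards most of the diary record and the run-in values, although the diary is handed out at Visit 1 and those values will exist.

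At stake is whatever the diary symptoms contribute to secondary endpoint 5, which section 24.4 frames as a comparison of active treatment with placebo.

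**Working it through.** The plan states no error rate, power or significance level for the contingency tables. The power figures in 24.9 concern transit only, so there is no planned figure to reproduce.

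**Inputs from the documents.** "Twelve female patients with functional constipation in each treatment group for a total of 36 patients", so 12 patients in each of 3 arms. Treatment lasts 14 days. Entry requires fewer than 3 complete spontaneous movements a week, that is, fewer than 6 in 14 days.

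**Assumptions, not in the documents.** Mean of 4 to 14 recorded movements of any kind per patient in the analysis window; within-patient ICC of 0.1 to 0.5; symptom prevalence 50%; test level 0.05 (section 24.1 gives 0.05 for the ANCOVA models only).

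**Reading A: each movement is a table entry.** With m movements per patient, the Pearson statistic is inflated by the design effect DEFF = 1 + (m − 1) × ICC. A 3 × 2 table has 2 degrees of freedom and critical value 5.991, so the actual level is

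P(χ²₂ > 5.991/DEFF) = exp(−2.996/DEFF) = 0.05^(1/DEFF).

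Example: m = 7 and ICC = 0.3 give DEFF = 1 + 6 × 0.3 = 2.8, and 0.05^(1/2.8) = 0.343.

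The formula assumes equal counts. A simulation under no drug effect (beta-binomial responses, Poisson counts with a minimum of 1, 2,500 trials per setting) allows counts to vary:

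| Mean movements | ICC | DEFF | Formula | Simulated |
|---|---|---|---|---|
| 4 | 0.1 | 1.3 | 0.100 | 0.117 |
| 4 | 0.3 | 1.9 | 0.207 | 0.250 |
| 4 | 0.5 | 2.5 | 0.302 | 0.377 |
| 7 | 0.1 | 1.6 | 0.154 | 0.172 |
| 7 | 0.3 | 2.8 | 0.343 | 0.380 |
| 7 | 0.5 | 4.0 | 0.473 | 0.527 |
| 10 | 0.1 | 1.9 | 0.207 | 0.222 |
| 10 | 0.3 | 3.7 | 0.445 | 0.482 |
| 10 | 0.5 | 5.5 | 0.580 | 0.618 |
| 14 | 0.1 | 2.3 | 0.272 | 0.287 |
| 14 | 0.3 | 4.9 | 0.543 | 0.566 |
| 14 | 0.5 | 7.5 | 0.671 | 0.698 |

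A second simulation let counts vary more between patients (gamma-Poisson, means 6 to 14). It gave 0.17 to 0.74 for a binary item over ICC 0.1 to 0.5, and 0.32 to 0.99 for the five-level straining item. With ICC 0 the rates were 0.04 to 0.06, so clustering is the cause.

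**Reading B: one categorised response per patient.** On the same kind of null data, a table of one dichotomised response per patient rejected in 0.056 to 0.078 of trials. This is a small-sample effect of the chi-square test, not clustering. The cost is power. With a mean of 7 movements, ICC 0.3 and an assumed log-odds shift of 1.2, power was 28% for this table and 51% for ANCOVA of the per-patient proportion with the run-in proportion as covariate. The size of that gap depends on assumptions. I reran it with the shift in one active arm, in both, or halved in one, at means of 4, 7 and 14 and ICC 0.1, 0.3 and 0.5. The ANCOVA was ahead in every setting.

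**Patient summaries compared directly.** Under the null, ANOVA of per-patient proportions rejected in 0.044 to 0.062 of trials, and Kruskal-Wallis on the per-patient mean straining score in 0.040 to 0.052.

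**The case against.** A reader might infer that the plan pools bowel movements, so that the symptom part of endpoint 5 runs far above a stated 5% error rate. The documents do not support that.

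- **Unit.** Section 24.6 never says that movements are the entries. Elsewhere a response is usually a patient's value: 24.2 imputes one per patient, and Table 6 uses the word for transit measures. The same sentence of 24.6 also covers the once-per-patient questionnaire.
- **Level.** Section 24.1 sets 0.05 for the ANCOVA models. No level is stated for the tables.
- **Endpoint.** The synopsis and 9.3 tie the diary to stool frequency and consistency, and the symptoms to the six-question survey. Section 24.6 does not name straining, emptying or blockage.
- **Window.** If the final diaries mean only the last day or so, there are few movements per patient and the inflation shrinks.
- **Detail elsewhere.** The synopsis refers exploratory efficacy analyses to an SAP, and no separate SAP text is available here.

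These points stand against the stronger reading, but they do not settle the matter. Section 24.6 explicitly draws symptom responses from the diaries as well as the questionnaires, and the diary's symptom entries exist only by movement. Even one final day can hold from zero to eight of them. If one response per patient is meant, the derivation rule is still missing and the run-in values still go unused. One sentence fixing one response per patient would cure the error rate but not the loss of information.

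**Conclusion.** The point holds as an unspecified unit of analysis combined with an unused baseline. It is not a finding that the plan pools movements.

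Under the movement-level reading, the false-positive rate for a binary item is about 11–70%, conditional on that reading and on the assumed ICC and movement counts. It is somewhat higher if counts vary more between patients, and higher again for straining. Under the patient-level reading, error is close to nominal, but power is lost relative to a baseline-adjusted patient summary (28% against 51% in the illustrated setting). The proposed analysis is better under either reading, so this is more than a request for missing detail.

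The reach is limited to the diary-symptom part of secondary endpoint 5. The primary endpoint, the frequency and consistency ANCOVAs and the survey items are unaffected.

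**What to change.** In 24.6, make the patient the unit for the diary symptoms. Before unblinding, define for each patient, over the treatment period:

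- the proportion of movements with complete emptying;
- the proportion of movements with blockage;
- the mean straining score.

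Compare arms on each by the ANCOVA already planned for consistency and ease of passage, on ranks if needed as 24.1 allows, with the patient's own run-in value as covariate. State the diary days that make up each period and the significance level used. Keep the contingency table for the survey items, where each patient contributes one answer.

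The cost is a few lines of plan text and a short derivation; the data are already collected. One small downside is that a patient with no movement in a period has no value for it. Consistency already has this problem, and the same handling rule should be written down for both.

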24.7 Analysis of pharmacokinetic and pharmacodynamic data

Pharmacokinetic and pharmacodynamic parameters will be analyzed as described in the SAP.

24.8 Analysis of safety

All safety variables and AEs will be presented, when possible, by treatment, with summary statistics.

All continuous variables will be described using standard statistical measures, i.e. number of observations, number of missing observations, mean, standard deviation, minimum and maximum value, median, 1st and 3rd quartile. All categorical variables will be summarized by absolute and relative frequencies.

24.9 Assessment of sample size

Table 1 below summarizes data for the primary response measures and uses the (relative) variation, (CV%) to estimate the effect size detectable with 80% power based on a two sample t-test at a two-sided alpha level of 0.05. The effect size is the difference in group means as a percentage of the overall mean for each response and assumes 12 subjects per group. The ANCOVA should provide 80% power to detect similar (pairwise) differences using a pooled estimate of variation across all three groups and potentially even smaller effect sizes by adjusting for important covariates. The data from the scintigraphic transit studies are based on the same methods proposed for this study. There is no planned adjustment for dropouts. In these types of studies, we expect less than five percent dropouts. Missing data will be handled by standard imputation methods (e.g. use of mean data for all participants for that specific missing data), with appropriate adjustment of the degrees of freedom for each data imputed.

Table 6 Primary Response Measurement Summary

Assuming n=12/ group		Effect Size [‡] (%)		
		Detectable(N=12 per group) with:		
Response Type	CV%	80% Power (α =0.05)		
GE solids t _{1/2} min [†]	25	27		
GC @ 24 hrs †	35	37		
‡ Effect Size is the difference between means	as a percentag	e of listed mean		

^{†*} Based on data from previous studies (31,32,33) using similar methods to those proposed here. Transit data[†] from C-IBS studies (e.g. Renzapride, prucalopride, Tegaserod).

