Since each of the primary endpoints assesses a separate hypothesis regarding the effects of A3309, no adjustment in the alpha level for testing multiple types of endpoints is anticipated, and a two-sided significance level of 0.05 will be used in each ANCOVA model.

Statistical Power

Based on data acquired using the same methods in the laboratory, the sample size of 12 patients per group provides 80% power to detect differences of approximately 27% to 37% in colonic transit, the primary endpoints. This magnitude of change is considered clinically significant.

Pharmacokinetic and Pharmacodynamic analyses

Plasma concentration of A3309 vs time curves will be plotted for each subject, on both linear/linear and log₁₀/linear scales. Mean plasma concentration vs time curves will also be presented by dose, PK and PD parameters.. Exploratory analyses of the PD variables will be conducted and described in the Statistical Analysis Plan (SAP).

Efficacy analyses

Exploratory analyses of the efficacy variables will be conducted and described in the Statistical Analysis Plan (SAP).

Analysis data sets

The primary analyses will follow the intent to treat (ITT) paradigm with all patients randomized included in the analyses. Those patients with missing response values will have their missing values imputed via the overall (patients with non-missing data) mean and a corresponding adjustment in the ANCOVA residual error variance degrees of freedom (subtracting one for each missing value imputed).

Safety data will be presented for all patients receiving investigational product.

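### With 12 patients per group, power for the stated 27% and 37% differences is about 70% by the plan's own t-test, and about 61% for the primary endpoint under the planned Dunnett comparison, not 80%

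*Combined protocol and SAP*

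**What the plan says.** The synopsis plans "Twelve female patients with functional constipation in each treatment group for a total of 36 patients". Section 24.9 takes CVs from previous transit studies to "estimate the effect size detectable with 80% power based on a two sample t-test at a two-sided alpha level of 0.05". It defines the scale: "The effect size is the difference in group means as a percentage of the overall mean for each response and assumes 12 subjects per group". In its footnote, Table 6 instead refers to the listed mean. That table has two rows:

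- gastric emptying half-time of solids: CV 25%, detectable difference 27%;
- GC24, the primary endpoint: CV 35%, detectable difference 37%.

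Section 24.9 extends the claim to the planned model: "The ANCOVA should provide 80% power to detect similar (pairwise) differences using a pooled estimate of variation across all three groups". It adds that covariates may allow smaller differences to be detected, and makes no allowance for dropouts.

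The synopsis summarizes this as "12 patients per group provides 80% power to detect differences of approximately 27% to 37% in colonic transit" and calls a change of that size clinically significant. Section 24.1 says that, if the overall ANCOVA p value is 0.10 or less, "both the 15 mg and 20 mg doses will be compared to placebo using" Dunnett's test.

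**The concern.** Every input to the calculation is given, so the printed differences can be checked, and they look too small for 12 per group. The calculation also uses an unadjusted two-group t-test, whereas the dose comparisons will use Dunnett's test, which has a larger critical value. In addition, the synopsis attaches the gastric emptying figure to colonic transit, which makes the power for the single primary endpoint look better than Table 6 itself shows.

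The stake is how a negative result is read. Section 12.1 describes the power as sufficient for clinically relevant differences, and Section 19.2 says that the results will inform the Phase 3 decision. If a true 37% change in GC24 has a 30% to 39% chance of being missed at a given dose rather than 20%, a non-significant dose comparison is weaker evidence of no effect than the plan implies.

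**Working it through.** **Inputs (Section 24.9 and Table 6).** n = 12 per group; two-sided alpha 0.05; target power 80%; CV 25% with difference 27%; CV 35% with difference 37%. If the CV and the difference are percentages of the same mean, the standardized difference is d = difference / CV:

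- gastric emptying: 27/25 = 1.080
- GC24: 37/35 = 1.057

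**Step 1: the plan's own test.** For a two-sample t-test, df = 2 × 12 − 2 = 22, the critical value is 2.074 and the noncentrality is d × √(12/2):

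- gastric emptying: 1.080 × 2.449 = 2.645, power 71.5%
- GC24: 1.057 × 2.449 = 2.589, power 69.7%

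Solving for 80% power gives d = 1.197, so the detectable differences are 25% × 1.197 = 29.9% and 35% × 1.197 = 41.9%. The stated 80% is not reproduced.

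**Step 2: can rounding or approximation explain it?**

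- Moving each CV and each difference by 0.5 gives 68% to 75% (gastric emptying) and 67% to 72% (GC24).
- The normal approximation gives 75.3% and 73.5%.
- Log-scale versions give 62% and 58% (increase), 85% and 89% (decrease), or 73% and 73% (symmetric). None gives 80% for both rows.

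**Step 3: pooled variance over three groups.** With df = 36 − 3 = 33, power is 72.8% and 71.0%, and the detectable differences are 29.5% and 41.2%. Pooling alone does not support the ANCOVA claim.

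**Step 4: the planned Dunnett comparison.** For two comparisons with a common control (correlation 0.5) and 33 df, the two-sided 5% critical value is about 2.31. Solving for 80% power gives d of about 1.29.

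| Test, n = 12 per group | Power, gastric emptying 27% | Power, GC24 37% | Detectable at 80% (gastric emptying / GC24) |
|---|---|---|---|
| t-test, 22 df | 71.5% | 69.7% | 29.9% / 41.9% |
| Pooled, 33 df, unadjusted | 72.8% | 71.0% | 29.5% / 41.2% |
| Dunnett, 33 df | 63.3% | 61.3% | 32.3% / 45.2% |

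A simulation that included the 0.10 overall test left the Dunnett power unchanged. If both doses truly produce a 37% difference in GC24, the chance of detecting at least one is about 77%, and of detecting both about 46%.

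**Step 5: what would give 27 and 37?** Fifteen per group at 80% power gives 26.5% and 37.1%. Twelve per group at 70% power also gives 26.5% and 37.1%. A one-sided 0.05 test with 12 per group gives 26.2% and 36.7%. All are close, but none is the calculation described, and the documents do not show whether any was used.

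**Step 6: the synopsis.** Table 6 gives one figure for colonic transit, 37%. The lower end of the synopsis range, 27%, is the gastric emptying row, and gastric emptying is a secondary endpoint.

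**The case against.** The strongest reply concerns the denominator. The text takes the difference relative to the overall mean, the footnote relative to the listed mean, and dividing the difference by the CV assumes one base for both. Suppose instead that the CV is relative to the placebo mean, that the difference is relative to the mean of all three groups, and that only one dose works. A difference of x relative to placebo is then x / (1 + x/3) of the overall mean: 0.299 / (1 + 0.299/3) = 27.2% and 0.419 / (1 + 0.419/3) = 36.8%, which match Table 6. This shows that the definition is ambiguous and the sponsor should settle it. It does not rescue the text as written. None of those assumptions is stated, the footnote contradicts them, and a two-sample calculation would use a two-group mean, which gives 26.0% and 34.6%. On that same favorable reading the printed 37% becomes 0.37 / (1 − 0.37/3) = 42.2% of the placebo mean, d = 0.422/0.35 = 1.206, and Dunnett power is still only about 74%.

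Second, covariates could recover power. The documents give no explained variance, so a range has to be assumed. R² of 0.1, 0.2 and 0.3 gives 75%, 80% and 85% for an unadjusted GC24 comparison, and 66%, 72% and 78% for Dunnett. The listed covariates are age, BMI and baseline diary summaries, not baseline GC24, so a large gain cannot be presumed.

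Third, planning on a pairwise t-test is a legitimate choice in a small pharmacodynamic study, and Section 24.9 names its test openly. That is fair: the Dunnett figure measures a mismatch between the planning test and the analysis, not an arithmetic slip. But Section 24.9 also claims 80% power for the ANCOVA pairwise differences, and Section 24.1 makes those comparisons by Dunnett's test.

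**Conclusion.** The concern holds. On the stated inputs, power is 71.5% for gastric emptying and 69.7% for GC24, about 8 to 10 percentage points below the claim. For the planned Dunnett comparison of a given dose, GC24 power is about 61%. The chance of missing a true 37% difference in the primary endpoint is therefore about 30% (t-test) to 39% (Dunnett), not 20%.

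The t-test figures assume that the CV and the difference share one base. The Dunnett figures also assume a familywise two-sided level of 0.05, which Section 24.1 does not state explicitly for that test, and no covariate gain. The misattribution of 27% to colonic transit in the synopsis stands on the documents alone.

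**What to change.** Keep 12 per group and correct the statements in Section 24.9 and the synopsis:

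- In Table 6, give detectable differences at 80% power of about 30% (gastric emptying) and 42% (GC24) for the unadjusted t-test, and about 32% and 45% for the Dunnett comparison. Equivalently, state that power for a 37% GC24 difference is about 70% unadjusted and 61% with Dunnett.
- Say which mean is the base for both the CV and the difference, and make the text and footnote agree. If a different base was used, state it with its assumptions and show the calculation.
- State the familywise level for Dunnett's test. If covariate gain is relied on, give the assumed R² and its source.
- In the synopsis, remove 27% from the colonic transit statement, or label it as gastric emptying.

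The cost is wording only: no extra patients, procedures or analyses. The stated sensitivity of the trial becomes less favorable.
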